
Note: The following hospitalizations are not considered SAEs in BMS clinical studies:
 
• a visit to the emergency room or other hospital department < 24 hours, that does not result in admission (unless considered an important medical or life-threatening event)• elective surgery, planned prior to signing consent• admissions as per protocol for a planned medical/surgical procedure• routine health assessment requiring admission for baseline/trending of health status (e.g., routine colonoscopy)• medical/surgical admission other than to remedy ill health and planned prior to entry into the study. Appropriate documentation is required in these cases• admission encountered for another life circumstance that carries no bearing on health status and requires no medical/surgical intervention (e.g., lack of housing, economic inadequacy, caregiver respite, family circumstances, administrative reason)• admission for administration of anticancer therapy in the absence of any other SAEs (applies to oncology protocols)	
Results in persistent or significant disability or permanent damage	
Is a congenital anomaly/birth defect	
Is an important medical event (defined as a medical event(s) that may not be immediately life-threatening or result in death or hospitalization but, based upon appropriate medical and scientific judgment, may jeopardize the participant or may require intervention [e.g., medical, surgical] to prevent one of the other serious outcomes listed in the definition above.) Examples of such events include, but are not limited to, intensive treatment in an emergency room or at home for allergic bronchospasm; blood dyscrasias or convulsions that do not result in hospitalization.) Potential drug induced liver injury (DILI) is also considered an important medical event. (See Section 8.2.7 for the definition of potential DILI.)	

Pregnancy and potential drug induced liver injury (DILI) must follow the same transmission timing and processes to BMS as used for SAEs (see section [8.2.5](#) for reporting pregnancies).

Any component of a study endpoint that is considered related to study therapy should be reported as a SAE (e.g., death is an endpoint; if death occurred due to anaphylaxis, anaphylaxis must be reported).

EVALUATING AES AND SAES

Assessment of Intensity

The intensity of AEs is determined by a physician and will use the following levels:
 
• Mild: An event that is easily tolerated by the subject, causing minimal discomfort, and not interfering with everyday activities.• Moderate: An event that causes sufficient discomfort and interferes with normal everyday activities.• Severe: An event that prevents normal everyday activities. An AE that is assessed as severe should not be confused with an SAE. Severe is a category utilized for rating the intensity of an event; and both AEs and SAEs can be assessed as severe.
Assessment of Causality

• The investigator is obligated to assess the relationship between study intervention and each occurrence of each AE/SAE. A “reasonable possibility of a relationship” conveys that there are facts, evidences, and/or arguments to suggest a causal relationship rather than a relationship cannot be ruled out.• The investigator will use clinical judgment to determine the relationship.• Alternative causes, such as underlying disease(s), concomitant therapy, and other risk factors, as well as the temporal relationship of the event to study intervention administration will be considered and investigated.• The investigator will also consult the Investigator’s Brochure (IB) and/or Product Information, for marketed products, in his/her assessment.• For each AE/SAE, the investigator must document in the medical notes that he/she has reviewed the AE/SAE and has provided an assessment of causality.• There may be situations in which an SAE has occurred and the investigator has minimal information to include in the initial report to Sponsor. However, it is very important that the investigator always make an assessment of causality for every event before the initial transmission of the SAE data to Sponsor.• The investigator may change his/her opinion of causality in light of follow-up information and send a SAE follow-up report with the updated causality assessment.• The causality assessment is one of the criteria used when determining regulatory reporting requirements.

Follow-up of AEs and SAEs

If only limited information is initially available, follow-up reports are required. Note: Follow-up SAE reports must include the same investigator term(s) initially reported.

If an ongoing SAE changes in its intensity or relationship to study treatment or if new information becomes available, the SAE report must be updated and submitted within 24 hours to BMS (or designee) using the same procedure used for transmitting the initial SAE report.

All SAEs must be followed to resolution or stabilization.

REPORTING OF SAEs TO SPONSOR OR DESIGNEE

SAEs, whether related or not related to study drug, and pregnancies must be reported to PRA Drug Safety within 24 hours of awareness of the event.

SAEs must be recorded on the SAE Report Form. For studies capturing SAEs through electronic data capture (EDC), electronic submission is the required method for reporting. In the event the electronic system is unavailable for transmission, paper forms must be used and submitted immediately. When paper forms are used, the original paper forms are to remain on site.

Pregnancies must be recorded on a paper Pregnancy Surveillance Form and transmitted via email or confirmed facsimile (fax) transmission to:

[REDACTED]
[REDACTED]
[REDACTED]
[REDACTED]
[REDACTED]
[REDACTED]

APPENDIX 4 WOMEN OF CHILDBEARING POTENTIAL DEFINITIONS AND METHODS OF CONTRACEPTION

DEFINITIONS

Woman of Childbearing Potential (WOCBP)

A woman is considered fertile following menarche and until becoming postmenopausal unless permanently sterile. Permanent sterilization methods include hysterectomy, bilateral salpingectomy, and bilateral oophorectomy.

Women in the Following Categories Are not Considered WOCBP

- Premenarchal
- Premenopausal female with 1 of the following:
 - Documented hysterectomy
 - Documented bilateral salpingectomy
 - Documented bilateral oophorectomy

Note: Documentation can come from the site personnel's review of the participant's medical records, medical examination, or medical history interview.

- Postmenopausal female
 - A postmenopausal state is defined as 12 months of amenorrhea in a woman over age 45 years in the absence of other biological or physiological causes. In addition, females under the age of 55 years must have a serum follicle stimulating hormone (FSH) level > 40 mIU/mL to confirm menopause.

Note: Females treated with hormone replacement therapy, (HRT) are likely to have artificially suppressed FSH levels and may require a washout period in order to obtain a physiologic FSH level. The duration of the washout period is a function of the type of HRT used. The duration of the washout period below are suggested guidelines and the investigators should use their judgment in checking serum FSH levels.

- 1 week minimum for vaginal hormonal products (rings, creams, gels)
- 4 week minimum for transdermal products
- 8 week minimum for oral products

Other parenteral products may require washout periods as long as 6 months. If the serum FSH level is > 40 mIU/ml at any time during the washout period, the woman can be considered postmenopausal.

CONTRACEPTION GUIDANCE FOR FEMALE PARTICIPANTS OF CHILD BEARING POTENTIAL

One of the highly effective methods of contraception listed below is required during study duration and until the end of relevant systemic exposure, defined as # Days/ Weeks Relevant Exposure days/weeks after the end of study treatment, plus 30 days.

Local laws and regulations may require use of alternative and/or additional contraception methods.

Highly Effective Methods That Are User Independent

- Nonhormonal intrauterine devices (IUDs), such as ParaGard ®
- Bilateral tubal occlusion
- Vasectomized partner

A vasectomized partner is a highly effective contraception method provided that the partner is the sole male sexual partner of the WOCBP and the absence of sperm has been confirmed. If not, an additional highly effective method of contraception should be used.

- Complete Sexual abstinence

Sexual abstinence is considered a highly effective method only if defined as refraining from heterosexual intercourse during the entire period of risk associated with the study treatment. The reliability of sexual abstinence needs to be evaluated in relation to the duration of the study and the preferred and usual lifestyle of the participant.

- Complete abstinence is an acceptable form of contraception for all study drugs and must be used throughout the duration of the study treatment (plus 5 half-lives of the investigational drug plus 30 days)
- It is not necessary to use any other method of contraception when complete abstinence is elected.
- WOCBP participants who choose complete abstinence must continue to have pregnancy tests, as specified in Section 2.
- Acceptable alternate methods of highly effective contraception must be discussed in the event that the WOCBP participants chooses to forego complete abstinence

Unacceptable Methods of Contraception

- Periodic abstinence (calendar, symptothermal, post-ovulation methods)
- Withdrawal (coitus interruptus)
- Spermicide only
- Lactation amenorrhea method (LAM)

- Progestogen-only oral hormonal contraception, where inhibition of ovulation is not the primary mechanism of action
- Hormonal methods of contraception including oral contraceptive pills containing combined estrogen + progesterone, vaginal ring, injectables, implants and IUDs such as Mirena ®
- Intrauterine hormone-releasing system (IUS)
- Diaphragm with spermicide
- Cervical cap with spermicide
- Vaginal Sponge with spermicide
- Male or female condom with or without spermicide*. Male and female condoms cannot be used simultaneously

CONTRACEPTION GUIDANCE FOR MALE PARTICIPANTS WITH PARTNER(S) OF CHILD BEARING POTENTIAL.

Male participants with female partners of childbearing potential are eligible to participate if they agree to the following during the treatment and until the end of relevant systemic exposure.

- Inform any and all partner(s) of their participation in a clinical drug study and the need to comply with contraception instructions as directed by the investigator.
- Male participants are required to use a condom for study duration and until 91 Days after discontinuation (duration of study drug plus 90 days [duration of sperm turnover] of treatment in the male participant).
- Female partners of males participating in the study to consider use of effective methods of contraception until 91 Days after discontinuation (duration of study drug plus 90 days [duration of sperm turnover] of treatment in the male participant).
- Male participants with a pregnant or breastfeeding partner must agree to remain abstinent from penile vaginal intercourse or use a male condom during each episode of penile penetration during the treatment and until 91 Days after discontinuation (duration of study drug plus 90 days [duration of sperm turnover] of treatment in the male participant).
- Refrain from donating sperm for the duration of the study treatment until 91 Days after discontinuation (duration of study drug plus 90 days [duration of sperm turnover] of treatment in the male participant).

COLLECTION OF PREGNANCY INFORMATION

Guidance for collection of Pregnancy Information and outcome of pregnancy on the Pregnancy Surveillance Form is provided in Section [8.2.5](#) and the [APPENDIX 3](#) for AE and SAE Definitions and procedures for Evaluating, Follow-up and Reporting.

3.0 Introduction

This Statistical Analysis Plan (SAP) describes the statistical methods that will be used during the analysis and reporting of data collected under Bristol-Myers Squibb Research and Development (BMS) Protocol CV013034.

This SAP should be read in conjunction with the study protocol and electronic case report form (eCRF). This version of the plan has been developed using the protocol dated 15-Apr-2019 (including all amendments up to this date) and the final eCRF(s) dated 22-Oct-2018.

An approved and signed SAP is a requirement for database lock.

This SAP only covers the results that will be processed by the PRA Early Development Services (EDS) Biostatistics Department.

PRA EDS will perform the efficacy, pharmacokinetic (PK), pharmacodynamic (PD), biomarker and safety and tolerability evaluations.

This SAP supersedes the statistical considerations identified in the protocol; where considerations are substantially different, they will be so identified. Any post-hoc or unplanned analyses, or significant changes from the planned analysis in this SAP performed to provide results for inclusion in the clinical study report (CSR) but not included in this SAP, will be clearly identified in the CSR. Changes to planned analyses do not require an updated SAP but should be discussed with the sponsor and included in the CSR if significant.

4.0 Changes from Previous Version of Approved SAP

This is the first version of the SAP.

5.0 Study Objectives

5.1 Primary

Evaluate the effects of HNO donor BMS-986231 on 4-hour urine output in patients with HFrEF after administration of 40 mg of IV furosemide.

5.1.1 Primary Endpoints

The total volume of urinary output 4 hours after 40 mg furosemide bolus given to patients with HFrEF while on BMS-986231 compared to placebo: absolute difference in total volume and % change from placebo.

5.2 Secondary

Assess the effect of BMS-986231 on fractional excretion of Na (FeNa)

Assess the effect of BMS-986231 on fractional excretion of K (FeK)

Assess the effects of BMS-986231 on furosemide urinary and plasma concentration and the ratio urinary sodium to urinary furosemide

Assess safety of BMS-986231

5.2.1 Secondary Endpoints

FeNa, FeK, furosemide urinary and plasma concentration and ratio urinary sodium to urinary furosemide at 8 hours post-start infusion. Parameter values while patient is on BMS-986231 compared to placebo: absolute differences and % change from placebo.

5.2.2 Safety Endpoint

[figure not shown]
Clinically relevant hypotension (defined as SBP < 90 mmHg or symptomatic hypotension) during infusion, incidence of AEs, abnormal clinical laboratory values, vital signs, ECGs, telemetry, physical examinations.

6.0 Study Design

This is a double blinded, randomized, two-way cross-over, placebo-controlled study to evaluate the effects of HNO donor BMS-986231 on 4-hour urine output in HFrEF patients after administration of 40 mg of IV furosemide. The study consists of 2 one-day treatment periods (BMS-986231 or placebo) separated by a washout period of at least 7 days (Day 2 to at least Day 8), but no more than 4 weeks. Each period includes 8-hour infusion. A standard dose of 40 mg IV furosemide will be administered by IV bolus injection at the midpoint (4 hour, H4) of an 8-hour infusion. Screening for inclusion in the study will be performed up to 4 weeks before the first treatment day (Day 1 of the first period). Approximately 20 subjects will be included. The total duration of the study will be approximately 8 weeks.

Study Design Schematic from Protocol:

6.1 Sample Size Considerations

The number of subjects to be enrolled was chosen based on practical considerations. Twenty patients with HFrEF will be randomized to one of 2 sequences: BMS-986231/furosemide followed by placebo/furosemide or placebo/furosemide followed by BMS-986231/furosemide. The difference between BMS-986231 and placebo in total urine output in the 4 hours following furosemide administration will be estimated and presented with 95% confidence intervals (CIs).

Normal healthy volunteers have a urinary output around 0.5-1.0 mL/kg/H (40-100 mL/H), which could be decreased in people over 65 years old or patients with HF at around 0.2-0.5 mL/kg/H (20-40 mL/H). Patients with HF given a bolus of IV loop diuretics is estimated to have their diuresis increased to 250-300 mL/H in the 4 hours following the administration. Assuming the standard deviation of urine output change is 20~35 mL/H based on the estimated range of the changes, with 20 patients, the study will be able to demonstrate a 20% increase in urinary output compared to placebo, with 90% power.

6.2 Randomization

The subjects were randomized by the Biostatistics Department of the EDS group of PRA Health Sciences using PROC PLAN in SAS. Subjects (N=20 plus 4 additional) were assigned to one of the two sequences active treatment/placebo or placebo/active treatment with a 1:1 allocation ratio. An additional randomization was run a second time for the second site (Richmond, London) which was only added to the study when it was already running at the first site (NHS, Glasgow). For details, please see Global Note to File no.2.

Subject numbers that were used are R01-R24 and S01-S24. Participants will not be replaced if they are discontinued from the study.

7.0 Overview of Planned Analysis

7.1 Changes from Protocol

There are no changes from protocol

7.2 Planned Analyses

7.2.1 Preliminary Analysis

No preliminary analysis is planned.

7.2.2 Topline Results

Topline tables, figures, and listings (TFLs) will be provided after database lock. Topline TFLs will be determined by the Biostatistics Asset Lead and Clinical Pharmacology Asset Lead prior to programming commencing and will be the minimal set of TFLs needed to analyze key endpoints.

7.2.3 Final Analysis

The full set of draft TFLs will be provided after topline TFLs. After comments have been incorporated on the draft TFLs, the TFLs will be approved by the Biostatistics Asset Lead and incorporated in the CSR.

8.0 Definitions and General Analysis Methods

8.1 Analysis Data Presentation

8.1.1 Rounding

In listings, data will be presented with the same precision as the original data. Derived data will be rounded for presentation purposes.

For all summaries (with the exception of PK), the mean will be presented to 1 decimal greater than the original data, the SD to 2 decimals greater than the original data, and the median, minimum (min) and maximum (max) values will be presented to the same number of decimal places as the original data.

For PK summaries, mean, SD, median, min, and max values ≥ 100 will be presented as integers, values < 100 but ≥ 10 will be presented with 1 decimal, values < 10 but ≥ 1 will be presented with 2 decimals, and values < 1 will be presented with 3 decimals. Ratios will be presented with 3 decimals. Coefficient of variation (%CV) will be presented with 1 decimal.

For listing presentation purposes, PK parameters will be rounded in the same manner as noted above for summaries.

P-values will be reported to 4 decimal places; p-values less than 0.0001 will be reported as p <0.0001.

8.1.2 Imputation

Unless otherwise noted, data will not be imputed.

8.1.3 Descriptive Statistics

Unless otherwise indicated in specific data type sections, continuous variables will be summarized with the following descriptive statistics: n (number of observations), (arithmetic) mean, SD, median, min, and max.

Categorical data will be summarized with frequencies and percentages. Percentages by categories will be based on the number of subjects within a treatment group. Percentages will be rounded to 1 decimal, except 100% which will be displayed without any decimal places. Percentages will not be displayed for zero counts. Categories will be presented in the tables exactly as they appear in the CRF / Database.

8.1.4 Pooling

No data will be pooled for this study.

8.1.5 Unscheduled Measurements

Unscheduled measurements will be included in the listings. With the exception of unscheduled measurements used for baseline, unscheduled measurements will be excluded from the descriptive statistics and statistical analysis.

8.2 Analysis Data Definitions

8.2.1 Baseline Definition

Unless otherwise stated, baseline for post-dose evaluations is defined as the last observation recorded before the study drug administration in a period. The last observation can be an unscheduled / repeated measurement.

8.2.2 Treatment/Subject Grouping

Label	Grouping
Study Drug	BMS-986231 or Placebo
Treatment	BMS-986231: BMS-986231 12 µg/kg/min for 8 hours (20 mL/H), single infusion IV Placebo: Placebo 20 mL/H for 8 hours, single infusion IV Furosemide: Furosemide 40 mg, single IV bolus

8.2.3 Common Variable Derivations

Variable	Dataset	Definition/Calculation
Change from Baseline	All	Post-dose Observation minus Baseline Observation
Analysis Period	All	Interval of time during which treatment is constant.
TEAE	AE	AE is a TEAE if the AE Date/Time is greater than or equal to the first Dose Date/Time

8.2.4 QC

The analysis datasets and the TFLs will be QC'd according to the PRA EDS QC plan that is developed according to the EDSREP 009 SOP.

8.2.4.1 Critical Data

The QC plan requires datasets be classified as critical or non-critical. The datasets considered critical are subject level, efficacy, and adverse events (ADSL, ADEFF, and ADAE).

8.2.5 ADaM Datasets and Metadata

The analysis datasets will be generated in accordance with Clinical Data Interchange Standard Consortium (CDISC) Analysis Data Model (ADaM) Version 2.1.

ADaM compliant datasets will be delivered to the sponsor. A define.xml file version 2 with the corresponding metadata will be included. Analysis results metadata are excluded.

8.3 Software

The statistical analysis and reporting will be done using SAS® for Windows™ Version 9.4 or higher (SAS Institute, Inc.).

PK parameter calculations will primarily be done using Phoenix® WinNonlin® Version 8.1 or higher (Certara, Inc.). Additional PK computations may be performed in SAS®.

8.4 Statistical Methods

8.4.1 Statistical Outlier Determination

No statistical outlier analysis is planned.

8.4.2 Predetermined Covariates and Prognostic Factors

There are no predetermined covariates or prognostic factors.

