ECG	X	ECGs should be recorded after the participant has been supine for at least 5 minutes. At screening, single ECGs will be recorded.
Laboratory Tests	X	Includes blood (hematology, serum chemistry, NT-proBNP or BNP [details in the protocol section]) and urine samples. Participants are required to fast for at least 10 hours prior to the collection of specimens for clinical laboratory tests (details in the protocol Section 8.4.6).
Pregnancy Test	X	For WOCBP only.

Table 2: On Treatment Procedural Outline (CV013-034)

Table 2: On Treatment Procedural Outline (CV013-034)

Procedure	Treatment Period			Notes
	Period 1 Day 1	Washout (7-28 days)	Period 2 Day 1	
		Washout between periods should be at least 7 days and no more than 4 weeks.		
Follow-up call/assessment	X		X	
To be done at Day 2 of each period. Will inquire about general status and occurrence of any AEs.
 
For each period, subjects must remain for at least 3.5 hours after the end of infusion^a. Patients may stay overnight or may be discharged the same day 3.5 hours after end of infusion^a if certain conditions are met (see Section 4.1 for details)

Laboratory Tests				
Hematology and Serum Chemistry	X		X	Laboratory tests will be performed in the morning of each treatment day (H0 [before start of infusion], H4 [just before furosemide bolus], and H8). See protocol Section 8.4.6 for details.
Pregnancy Test (WOCBP only)	X		X	
Blood sampling for PK (furosemide and BMS-986231 [and its metabolites])	X		X	
Blood sampling for PK will be done at H0 (before start of infusion), H2 and at H4 hours (just before furosemide bolus), H5, H6, H8 (or end of infusion^a) and H10 (2 hours after the end of the infusion^a) in each treatment period.
 
In addition, PK samples should be taken when the dose is lowered or discontinued (see protocol Section 8.5).

Blood sampling for Na, K, bicarbonate, creatinine, and eGFR	X		X	Blood sampling for Na, K, bicarbonate, creatinine, and eGFR will be done at H0 (before start of infusion), H4 (just before furosemide bolus), H5, H6, H7, H8 (or end of infusion ^a) in each treatment period.
Urine sampling for furosemide and BMS-986231 (or its metabolites)	X		X	Urine samples can be taken from the urine collection intervals done for the urinary output (see Table 8 in Section 8.5.1). An aliquot for both sets of metabolites and a back-up will be required for the analysis.

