5.3 Lifestyle Restrictions

5.3.1 Meals and Dietary Restrictions

Study participants will be asked to eat their usual diet, but it should remain similar for the 3 days prior to the infusion. Patients should keep a 3-day diet diary to record what they consume. During the infusion, study participants will be given up to 200 mL / hour as fluid intake, as tolerated. Urinary output will be collected every 2 hours in the first 4 hours and then hourly from 4 hours to 8 hours after start of infusion.

On each treatment day standardized meals and snacks will be served. No fasting is required the evening prior to each treatment day.

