15.0 Efficacy Analyses

15.1 Effect of BMS-986231 on urine output

All primary efficacy analyses will be performed using the treated (per protocol) population.

Urinary output will be listed by timepoint.

The volumes (total within 4 h after furosemide dosing, total within 4 h before furosemide dosing, total within 8 h after start of BMS-986231/placebo dosing and difference of totals after and before furosemide dosing) after BMS-986231 and after placebo will be calculated per patient.

Descriptive statistics (n, mean, SD, %CV, median, min, and max) will be used to summarize the absolute difference between the volumes under BMS-986231 dosing and under placebo and the percent change from placebo under BMS-986231 dosing of urinary output by treatment.

Plots of the arithmetic mean urinary output + SD by scheduled sampling times will be provided by treatment. Bar plots showing the arithmetic mean urinary output and the individual urinary output by interval and treatment will be provided. These plots will show time in hours. The plots will match the summary table results. Plots will be presented to the last scheduled time point.

A within patient analysis using a paired T-test will be performed to compare the volumes of urinary excretion and to test if there is a significantly different amount of urine secreted while receiving BMS-986231 versus placebo. Body weight might be considered as covariate, if significant.

The SAS PROC TTEST code is as follows:

```
proc ttest data = volume;  
  PAIRED BMS-986231*placebo;  
run;
```

Paired profiles and Q-Q plot of the urinary output under BMS-986231 and placebo treatment will be provided for a visual representation of the data.

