15.2 Effect of BMS-986231 on fractional excretion

Secondary efficacy analyses will be performed using the per protocol population.

The fractional excretion (total within 4 h after furosemide dosing, total within 4 h before furosemide dosing, total within 8 h after start of BMS-986231/placebo dosing and difference of totals after and before furosemide dosing) of Na (FeNa) and K (FeK) after BMS-986231 and after placebo will be calculated per patient.

Descriptive statistics (n, mean, SD, %CV, median, min, and max) will be used to summarize the absolute difference between the excretion under BMS-986231 dosing and under placebo and the percent change from placebo under BMS-986231 dosing of fractional excretion by treatment.

Bar plots showing the arithmetic mean urinary output and the individual urinary output by interval and treatment will be provided.

A within patient analysis using a paired T-test will be performed to compare the volumes of urinary excretion and to test if there is a significantly different amount of urine secreted while receiving BMS-986231 versus placebo.

Paired profiles of fractional excretion will be provided for a visual representation of the data.

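### The paired FeNa and FeK tests in SAP 15.2 leave out a pre-infusion baseline that can be derived in each period, at a possible cost in precision on secondary endpoints

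*SAP*

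**What the plan says.** **The analysis.** SAP 15.2 derives four versions of FeNa and FeK per patient and treatment: the total over the 4 hours after furosemide, then "total within 4 h before furosemide dosing, total within 8 h after start of BMS-986231/placebo dosing and difference of totals after and before furosemide dosing". The test is described as follows: "A within patient analysis using a paired T-test will be performed to compare the volumes of urinary excretion". That sentence speaks of volumes, but it stands in the fractional-excretion section, and SAP Appendix 4 lists a statistical analysis of fractional excretion (Table 14.2.2.3). I therefore read it as the FeNa and FeK test. It names no covariate and no pre-infusion value.

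**The covariate rule.** SAP 8.4.2 says "There are no predetermined covariates or prognostic factors". For urine output, SAP 15.1 adds "Body weight might be considered as covariate, if significant", but the code printed there is a paired t-test, "PAIRED BMS-986231*placebo".

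**The data.** Protocol Table 2 says, for each period, "Blood sampling for Na, K, bicarbonate, creatinine, and eGFR will be done at H0 (before start of infusion), H4", with further samples later. Protocol Table 8 has a urine row before the start of infusion, and its title names Na, K and creatinine among the assays. Protocol 1.3 starts that sampling within the hour before dosing. SAP 8.2.1 and Protocol 9.4 define baseline as the last value before dosing in the period.

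**The concern.** The two periods are 7 to 28 days apart. On diet, Protocol 5.3.1 says "Study participants will be asked to eat their usual diet, but it should remain similar for the 3 days prior to the infusion". A patient can still arrive at the two periods in different states of sodium and potassium handling. Any such difference passes straight into that patient's BMS-986231-minus-placebo difference, where the paired t-test treats it as noise. With about 20 pairs, the mean baseline difference between treatments also varies by chance, with a standard error of 1/√20 = 0.22 of its own SD.

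A value measured before the infusion could take out part of this noise, and it cannot absorb the drug effect of the same period. What is at stake is the width of the intervals for FeNa and FeK. The primary endpoint, the direction of the estimates and the error rate of the test are not at stake.

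**Working it through.** **1. Can a baseline be derived?** Fractional excretion is a ratio of concentrations: FeNa (%) = 100 × (urine Na × blood creatinine) / (blood Na × urine creatinine), and likewise for K. It needs no urine volume, so an untimed pre-infusion void is enough. Both urine concentrations come from the pre-infusion row of Protocol Table 8, and both blood values from H0 in Protocol Table 2.

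**2. Does the window before furosemide serve instead?** No. Furosemide is given at hour 4 of the infusion, so that window is hours 0 to 4 on study drug. Subtracting it can remove part of any drug effect already present.

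**3. The plan's own figure.** None is stated for FeNa or FeK. The only one is 90% power for a 20% rise in urine output with 20 patients. A 20% rise on 250–300 mL/H is 50–60 mL/H. With an SD of 20–35 mL/H, a paired t-test (n = 20, two-sided 0.05) has power above 99.9% even at 50 and 35, so 90% is not reproduced. That concerns a different endpoint and does not bear on this point.

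**4. The comparison.** Let D be the within-patient treatment difference in outcome, B the same difference in the pre-infusion value, and ρ their correlation (assumed; range 0 to 0.7).

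- Planned half-width: t(19) × SD(D) / √n, with t(19) = 2.093.
- Adjusted, D = τ + βB + error: half-width for τ at B = 0 is t(18) × SD(residual) × √(1/n + B̄²/S_BB), where B̄ is the mean of B, S_BB its centred sum of squares, and t(18) = 2.101.

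For normal data the residual SD is √(1−ρ²) of SD(D), and nB̄²/S_BB averages 1/(n−3) = 1/17. The ratio of widths is then about

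(2.101/2.093) × √(1 + 1/17) × √(1−ρ²) = 1.004 × 1.029 × √(1−ρ²) = 1.033 × √(1−ρ²).

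It equals 1 when ρ² = 1 − 1/1.033² = 0.063, so break-even is ρ = 0.25.

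**5. Results.** Simulation used 20,000 trials per setting. The true effect was set so that the unadjusted test has 80% power.

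| ρ | Formula, n=20 | Simulated width ratio, n=20 | Adjusted power, n=20 | Simulated width ratio, n=16 | Adjusted power, n=16 |
|---|---|---|---|---|---|
| 0 | 1.033 | 1.031 | 77.9% | 1.041 | 76.9% |
| 0.2 | 1.012 | 1.010 | 79.3% | 1.021 | 79.0% |
| 0.25 | 1.000 | 0.999 | – | – | – |
| 0.3 | 0.985 | 0.984 | 81.6% | 0.992 | 80.1% |
| 0.5 | 0.895 | 0.894 | 88.4% | 0.900 | 87.2% |
| 0.7 | 0.738 | 0.738 | 96.5% | 0.745 | 96.1% |

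Type I error lay between 4.7% and 5.5% for both analyses. A ratio of 0.894 is worth 20/0.894² = 25 patients instead of 20. The n = 16 columns are an assumed case, shown because SAP 15.2 uses the per-protocol set, which may be smaller than 20.

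**The case against.** **The gain may be small.** The planned test is valid, and below a correlation of about 0.25 the adjustment widens the interval. There are reasons to expect a weak correlation: the baseline is a spot pre-dose void, the outcome is a 4-hour response to 40 mg of IV furosemide, and patients take chronic loop diuretics, so a pre-infusion value may reflect the last home dose. The plan also limits drift through similar diet over three days, a diet diary, standardised meals on treatment days and stable heart-failure therapy. Random order guards against systematic imbalance. All of this stands. It makes the size of the gain uncertain and confines the point to precision. It does not explain why a baseline that the SAP defines and the trial can derive goes unused, when the simulated loss is at most about 3% to 4% of CI width.

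**A reader might infer that the SAP forbids covariates.** It does not. Section 8.4.2 says that none are predetermined, and 15.1 leaves body weight open. The omission comes from the choice of test in 15.2.

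**A reader might also infer that site belongs in the models**, because SAP 6.2 says "An additional randomization was run a second time for the second site". The documents do not support this. Both of a patient's treatments are compared within that patient, so a site difference in level cancels. With site shifts of 0, 1 and 5 within-period SDs and splits of 10:10 and 14:6, the paired t-test kept a type I error of 4.8% to 5.1%, and adding site changed power by at most about 0.3 percentage points. Site would matter only if the treatment effect, or a period effect, differed between sites, and nothing in the documents suggests that. SAP 6.2 gives a practical reason for the second list: the site joined while the study was running.

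**Conclusion.** The point holds as an optional improvement to the secondary analyses. The FeNa and FeK tests use no treatment-free value although one can be derived in each period. The possible gain is a CI about 11% narrower at a correlation of 0.5 and 26% narrower at 0.7. The possible loss is about 3% with 20 patients, or 4% with 16, if the baseline carries no information.

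These figures rest on an assumed correlation, approximately normal differences and a linear relation. They also assume that nothing carries over from the first period into the second period's baseline, which the washout is meant to secure. The documents give no SD or correlation for FeNa or FeK, so the gain cannot be narrowed further. The validity of the planned test is not in question.

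A related inconsistency is certain: 8.4.2 names no covariate, while 15.1 would admit body weight depending on its significance in the data, and the printed code has no place for it.

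**What to change.** - **SAP 15.2.** For the 4-hour post-furosemide FeNa, and separately FeK, regress the within-patient BMS-986231-minus-placebo difference on the BMS-986231-minus-placebo difference in the pre-infusion value. Take the intercept, at zero baseline difference, as the treatment effect with its 95% CI. Keep the unadjusted paired t-test as a sensitivity analysis.
- **Outcome.** State which of the four derived quantities is tested. SAP 5.2.1 places these endpoints at 8 hours after the start of infusion, so align the two sections. Correct the test sentence so that it refers to fractional excretion and not volumes.
- **SAP 8.4.2.** Name the pre-infusion difference as the covariate for FeNa and FeK.
- **SAP 15.1.** Either say in advance whether and how body weight enters, with code that can fit it, or delete the sentence.

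The cost is a few lines of SAP text, one short regression per endpoint and one degree of freedom. No new data are needed. The change should be fixed before database lock.
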